6.1 Population characteristics

All variables in this section will be analyzed descriptively. The analyses will be based on the FAS and pPPS, unless otherwise specified.

Any table displaying demographics and baseline characteristics will be repeated for the following COVID-19 pandemic related subgroups:

all randomized subjects affected by COVID-19 pandemic related study disruption
all randomized subjects with COVID-19 adverse event and/or positive SARS-CoV-2 PCR test
and/or positive serology IgG test after start of treatment

6.1.1 Subject disposition and validity

All except one table in this section will be based on all enrolled subjects.

For each investigator, the number of screening failures and the number of protocol deviations and prematurely discontinuations of randomized subjects will be presented in total and per individual treatment group. The screening failures, discontinued subjects and protocol deviations will be listed along with the reasons, where applicable, each. In particular, the number of participants who prematurely discontinue the study for any COVID-19 pandemic-related reason, as well as the reasons for premature discontinuation of study will be reported. An additional listing will show the inclusion and exclusion criteria not met.

Participants who completed the study will be summarized. A participant completed the study if she completed all phases of the study including the last visit.

In addition, a disposition summary by study period (epoch), i.e. screening, treatment, and follow-up, will show the number of subjects completing the respective epoch and the number of subjects discontinuing it prematurely including information of the reasons for discontinuation. The table will include COVID-19 pandemic associated reasons for discontinuation, i.e. the information whether decision for discontinuation was made by the participant, the physician or was due to logistical reasons. An overview of the subject disposition including the number of participants who received at least one dose of study drug will be given overall and by treatment group.

For each investigator, the number of randomized participants valid for the SAF, the FAS, the PPS and the PKS will be presented in total and per treatment group.

An overview of the subject validity and the primary reasons for exclusion from the respective analysis set will be given overall and by treatment group for the FAS only. A listing of the subjects' assignment to the (p)FAS, (p)PPS, SAF and PKS and the reasons for exclusion will also be provided by treatment group.

6.1.2 Demographics and Baseline Characteristics

The following demographic data and baseline characteristics will be summarized:

Age at baseline (years);
Age category (<30years vs 30-40years vs >40-55years);
Race;
Ethnicity;
Height (cm);
Subject rescreened;
Natural hair color (at age 18);
Main eye color;
Weight (kg) at baseline;
BMI (kg/m²) at baseline;
Reproductive and menstrual history;

Endometriosis history/characteristics

- Age at first endometriosis treatment (medical or surgical whatever is earlier);
- Previous medical treatments;
- Number of surgeries;

Baseline pain

- Mean worst pain;
- Nonmenstrual pelvic pain (NMPP);
- Dysmenorrhea;

Bleeding characteristics;

Baseline scores of EIS.

Demographic variables and baseline characteristics will be summarized using descriptive statistics and will be reported for the FAS and PPS.

6.1.3 Medical history

Medical history findings will be coded according to the latest effective version of the Medical Dictionary for Regulatory Activities (MedDRA), Medical history findings (id est, previous diagnoses, diseases or surgeries starting before signing of the informed consent) considered relevant to the study will be summarized by primary system organ class (SOC) and preferred term overall and per treatment group. The table will be calculated based on the SAF and the FAS, respectively.

6.1.4 Prior and concomitant medication

The number of participants that used prior and concomitant medication will be analyzed using frequency tables based on classified data. The classification will be done according to the World Health Organization Drug Dictionary (WHO-DD) and Bayer Drug Grouping (BDG).

This includes a classification of the substances which will be used for presentation, such as medication prohibited due to potential drug-drug interaction (E.g. Analgesia producing opioids and Nonsteroidal anti-inflammatory drugs (NSAIDs)).

The tables will display the following three categories: prior, prior/concomitant and post-treatment.

Regarding medication data collected during the study course, the following rules will be implemented:

If the stop time of medication is before the time of the first study drug administration, then medication is considered to be **prior** medication.

If the start time of medication is before or at the time of the first study drug administration and the stop time of medication is after or at the time of the first study drug administration then the medication is considered to be **concomitant** medication.

If the start time of medication is at or after the time of the first study drug administration and earlier than 14 days after or at the time of the last study drug administration, then the medication is considered to be **concomitant** medication.

If the start time of medication is later than 14 days after the time of the last study drug administration, then the medication is considered to be **post-treatment** medication.

If time information is missing but only date information is given, then classification of medication as prior or concomitant will be done by date information only. In such case, if the start day of medication is the same date as the first study drug administration, then the medication will be classified as concomitant medication.

Analysis of prior and concomitant medication will be performed on the SAF. Prior, concomitant and post-treatment medication will be shown by treatment group and total.

6.2 Efficacy

6.2.1 Primary Efficacy Endpoint

The primary efficacy endpoint is defined below along with other attributes of the primary estimand.

Primary Estimand

Endpoint: The primary efficacy variable will be the absolute change in mean worst EAPP from baseline (last 28 days before the first intake of study drug) to end of intervention (last 28 days ending with the last intake of study drug planned on Day 84 (+3)). The worst EAPP will be measured daily on the NRS by item 1 of the ESD. The time frame of 28 days captures a menstrual cycle on average. For more details on how to derive the mean values over 28 days see Section 4.5.

Summary measure: A population-level treatment group summary is an estimated model-based group mean of the primary endpoint's values adjusted for region (Japan vs. ROW excluding China) and a baseline EAPP. Treatment effect will be evaluated as a difference between group means.

Treatment: The investigated treatments will be BAY 1817080 25 mg or 75 mg or 150 mg or placebo, plus standardized rescue medication taken for any reason.

Population: The target population is comprised of women with surgically confirmed symptomatic endometriosis as further defined by the inclusion/exclusion criteria described in the study protocol.

Intercurrent events (IEs):

- a) Early discontinuation of study intervention:
 - o The IEs of premature discontinuation of study treatment due to a non-COVID-19-related AE and a premature discontinuation of study treatment due to a lack of efficacy will be considered as treatment failure and as such addressed by the composite strategy. The baseline value and the pre-discontinuation value will be considered as representative of the unfavorable outcomes associated with these events, respectively. Returning to baseline pain level is considered to be a clinically plausible outcome for participants not being able or willing to take the study treatment because of an AE and is considered to be an unfavorable outcome. The pre-discontinuation value reflects the pain level that the participant feels unfavorable enough to discontinue the study treatment due to a lack of efficacy.

For premature discontinuation of study treatment due to a non-COVID-19-related AE, the baseline value will be imputed as:

- a) If at least 15 observations are collected in the cycle in which the IE occurs: a weighted average of the observed values and the baseline value will be calculated for the current cycle, with the weights being number of available days divided by 28 days and number of missing days divided by 28 days. The baseline value will be used for the subsequent cycles.
- b) If less than 15 observations are collected in the cycle in which the IE occurs: the baseline value will be used for this and the subsequent cycles.

For premature discontinuation of study treatment due to a lack of efficacy the last observation will be carried forward.

- o The IEs of early discontinuation of the study intervention due to any other reason, including COVID-19 related reasons, will be addressed by the hypothetical strategy. The assumed hypothetical scenario is that participants would not discontinue the study treatment at that time and would have similar outcomes as other participants in the study. If a participant continues completing the e-diary, the information included after the IE will be discarded.
- b) The IEs of non-compliance with study intervention will be addressed using the treatment policy strategy: compliance will be calculated for each period between two consecutive visits. If the compliance is too low (i.e. below 80%), or too high (i.e. >120%, which is highly unlikely) for some but not all post-baseline cycles, the data collected during these no-compliant periods will be used as observed.
- c) Increased and decreased intake of standardized rescue medication taken for EAPP and taken for any other reason than EAPP will be addressed by the treatment policy strategy. Earlier trials suggest that the intake of standardized rescue medication taken for EAPP is expected to be low. Any change in intake of standardized rescue medication taken for either EAPP or other reasons is considered as part of a general background treatment. Consequently, the treatment policy strategy will be used, and the standardized rescue medication is specified as part of the treatment attribute.

Other potential IEs (e. g. pregnancy or death due to any cause, including COVID-19 infection, or surgery) are considered to be unlikely. The occurrence of unexpected IEs will be evaluated during the blinded review and the estimand definition will be amended if needed.

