7.1 Discontinuation of Study Intervention

In rare instances, it may be necessary for a participant to permanently discontinue study intervention. If study intervention is permanently discontinued, the participant will remain in the study, receive the procedures scheduled for the end of intervention visit (i.e. visit 5) as soon as possible, and then be evaluated for the whole follow-up phase. See the SoA for data to be collected at the time of discontinuation of study intervention and follow-up and for any further evaluations that need to be completed.

- Participants must discontinue study intervention if any of the following occurs:
 - o In the investigator's opinion, continuation of the study intervention would be harmful to the participant's well-being
 - Surgical treatment of endometriosis⁹
 - o Liver safety-related discontinuation criteria are met (see Section 10.6)
 - o Pregnancy (see Sections 8.3.5 and 10.4)
 - At the specific request of the sponsor and in liaison with the investigator (e.g. obvious non-compliance, safety concerns)
- Participants may be withdrawn from study intervention if any of the inclusion criteria are no longer fulfilled or if any of the exclusion criteria apply during treatment.

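### In the cycle of an adverse-event stop, the composite rule weights by diary entries present or absent, not by days before or after stopping

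*SAP*

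**What the plan says.** SAP Section 6.2.1 says that stopping study treatment for a non-COVID-19 AE, or for lack of efficacy, "will be considered as treatment failure and as such addressed by the composite strategy". For the AE case the baseline value stands for the unfavourable outcome.

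The AE rule has two branches. "If at least 15 observations are collected in the cycle in which the IE occurs" (IE is the intercurrent event), the cycle value is a weighted average of observed and baseline pain, "with the weights being number of available days divided by 28 days and number of missing days divided by 28 days". For later cycles, "The baseline value will be used for the subsequent cycles". With fewer than 15 observations, "the baseline value will be used for this and the subsequent cycles". Neither the weights nor the threshold refers to treatment status.

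For discontinuation for any other reason (hypothetical strategy), the SAP adds: "If a participant continues completing the e-diary, the information included after the IE will be discarded". The AE rule has no such sentence.

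Protocol Section 7.1 provides for data after the stop: "If study intervention is permanently discontinued, the participant will remain in the study", with Visit 5 as soon as possible and then the whole follow-up phase. In the Schedule of Activities the diary is daily and the device is returned only at Visit 6 or 7.

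The cycle itself is described in two ways. The endpoint in SAP 6.2.1 is the 28 days up to the last intake, and SAP Section 4.5 counts back from end of treatment. The footnotes in Protocol Section 3 and the worked examples in SAP 4.5 use the fixed days 1-28, 29-56 and 57-84.

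**The concern.** If stopping for an AE is a failure represented by baseline pain, baseline should stand in for the days after the stop. The rule instead lets it stand in for days without a diary entry. The two agree only if the diary is complete up to the stop and empty afterwards.

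They can differ in two directions. Entries kept after the stop displace baseline, so a woman whose pain off drug remains low keeps her improvement. Entries missed before the stop are filled with baseline, so a diary gap is scored as failure. The primary contrast uses the Visit 5 means, so two women with the same event and the same pain can receive different primary values because of diary habits. SAP Section 7 records that sensitivity analyses were removed, so no specified analysis would show this dependence.

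**Working it through.** **The plan's own figure.** Protocol Section 9.2 states about 90% average power with 50 per group, SD 2.5 and one-sided alpha 0.10. Simulating the maximum-contrast test for the four candidate curves gives 0.891, 0.894, 0.932 and 0.910, mean 0.906. The figure is reproduced and does not depend on this rule.

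**Inputs.** From the documents: 28-day cycle, 15-entry threshold, primary value at Visit 5. Assumed: mean change from baseline of -3 on drug and -2 in diary entries after stopping. The day of the stop counts as an on-drug day.

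**Formulas (change from baseline, so a baseline value contributes 0).**

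- As written: sum of the changes on all available days in the event cycle / 28 if there are at least 15 entries, otherwise 0.
- By treatment days: (pre-event days / 28) x mean pre-event change.

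**Fixed blocks, event in days 57-84.**

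| Stop and diary | As written | By treatment days |
|---|---|---|
| Day 60, complete diary | (4 x -3 + 24 x -2)/28 = -2.14 | 4/28 x -3 = -0.43 |
| Day 70, complete diary | (14 x -3 + 14 x -2)/28 = -2.50 | 14/28 x -3 = -1.50 |
| Day 60, complete diary, pain back at baseline off drug | (4 x -3 + 24 x 0)/28 = -0.43 | -0.43 |
| Day 60, diary ends at the stop | 4 entries, below 15: 0 | -0.43 |
| Day 78, 7 of 22 on-drug days missed, none after | 15 x -3/28 = -1.61 | 22/28 x -3 = -2.36 |
| Day 78, same gaps, 6 entries after | (15 x -3 + 6 x -2)/28 = -2.04 | -2.36 |

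For a stop on days 1-56, Visit 5 belongs to a later cycle and takes baseline (change 0) however the diary is kept. Only the event-cycle value, at an earlier visit in the mixed model, is affected.

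**Window ending at last intake.** No day after the stop falls in the event cycle, so every missing day is an on-drug gap. With 7 of 28 days missed the rule gives 21/28 x -3 = -2.25. A woman with the same gaps and no AE stop gets the mean of her available entries, -3.00 (SAP Section 4.3.2).

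**Arm mean, if 5% of an arm stop for an AE in the last cycle (assumed; fixed blocks).**

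- Complete diaries: 0.05 x (2.50 - 1.50) = 0.05 to 0.05 x (2.14 - 0.43) = 0.09 points too favourable.
- Day 78 with gaps and no later entries: 0.05 x (2.36 - 1.61) = 0.04 points too unfavourable.
- If the reference also applies the 15-entry threshold to pre-event entries, the day 60 and day 70 stops have 4 and 14 entries and score 0. The complete-diary difference is then 0.05 x 2.14 = 0.11 to 0.05 x 2.50 = 0.13.

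For scale, the planned maximum effect is 1.2 points, so 0.05 to 0.09 is 4% to 7% of it. One arm's standard error is 2.5/√50 = 0.35.

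**The case against.** The strongest objection concerns the window. If the endpoint window ends at last intake, entries after the stop are follow-up data, which have their own 28-day intervals in SAP Section 6.2.3.1, and no woman carries them into her primary value. This has support in SAP 6.2.1 and 4.5, so the loss of the failure score through post-stop entries cannot be called the only reading. But the AE rule speaks of the cycle of the event and of subsequent cycles, which fits fixed blocks. Under the last-intake window, baseline would enter that cycle only through on-drug gaps. The rule misfires on either reading.

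It can also be said that the purpose is plain: SAP Section 7 says the text was expanded to clarify imputation after an intercurrent event, so missing days may have been meant as post-event days. That may be the intention, but a programmer would have to supply it.

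The reach is narrow. The sponsor halted treatment, and stops caused by the halt fall under the other-reason bullet, where discarding is explicit. The documents give no AE-stop rate; 5% in the last cycle alone would mean about 15% over 84 days if stops were evenly spread (5% x 84/28). The shift is at most about a quarter of one arm's standard error (0.09/0.35). All of this stands and limits the size of the point.

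A reader might also infer that any woman who stops for an AE and keeps her diary escapes being scored as a failure, or that missed diary days in general are set to baseline. The text supports neither. Later cycles take baseline, and the gap penalty applies only in the event cycle of a woman who stops for an AE.

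**Conclusion.** The point holds within limits. The AE rule ties the composite score in the event cycle to diary completion, and it lacks the discard sentence given for the hypothetical strategy. Under fixed blocks, only last-cycle stops reach the Visit 5 value, and the failure is lost only as far as pain off drug stays below baseline; if pain returns fully to baseline, the written rule and treatment-day weights agree. Under a last-intake window, the fault is the penalty on diary gaps.

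The size is modest: 0.05 to 0.09 points on an arm mean against treatment-day weights, assuming 5% last-cycle AE stops, complete diaries and changes of -3 on drug and -2 off drug.

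It is tempting to conclude that the error favours the higher doses, or that the composite strategy is not estimated at all. The documents do not support either. They give no AE-stop rates by arm, the two errors pull in opposite directions, and women who stop in the first two blocks are scored as intended at Visit 5. The stated power and sample size are not in question.

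**What to change.** For discontinuation due to a non-COVID-19 AE, amend SAP Section 6.2.1 to:

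- discard diary entries after the event, as for the hypothetical strategy;
- weight the mean of available pre-event entries by pre-event days/28, and the baseline value by post-event days/28;
- treat missed pre-event days as ordinary missing diary days, as in Section 4.3.2;
- state that the 15-entry threshold counts pre-event entries only.

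State in both 6.2.1 and 4.5 that cycles for these women are fixed blocks from start of treatment (days 1-28, 29-56, 57-84), as an explicit exception to the window ending at last intake.

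The cost is SAP wording and a small program change. Scoring the failures as intended may also cost some power. Suppose last-cycle AE stops rise in equal steps from 0 on placebo to 5% at 150 mg, with stop days evenly spread and a change of -3.5 for every woman who stops. Average power would fall from 0.906 to 0.870 with treatment-day weights, or 0.830 if every such stop scored full baseline. With the 15-entry threshold the rule lies between. That loss belongs to the chosen estimand and is no reason to keep the present wording.

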6.2.1.1 Primary efficacy Analysis

The primary analysis will be performed on the pPPS analysis set as defined in Section 5.1.

For the primary efficacy variable, it is planned to perform a test for a dose-response signal in the study population, under the assumption of a monotone dose-response relationship in the dose range considered. The MCP-Mod method [5] combining multiple comparison procedures principles with modeling techniques (MCP-Mod) will be used for the primary analysis of the primary efficacy variable. This method allows the flexibility of modeling for dose estimation, while preserving the robustness to model misspecification associated with MCP procedures. More specifically, it is planned to use a generalization of the original MCP-

Mod method which allows to perform dose-response testing and modeling in conjunction with the response variable being described by a parametric model [6]. The key idea of this generalization is to decouple the dose-response model from the expected response so that the dose response can be characterized using a suitable parameter in the probability distribution of the response.

Assumptions

It is assumed that the primary efficacy variable, denoted as Y , is measured at the patient level for the 4 parallel groups corresponding to dose levels: (placebo =) $d_1 < d_2 < \dots < d_K$, where $K = 4$.

Furthermore, assume that the probability model for the patient responses Y includes parameters $\mu_{d_1}, \dots, \mu_{d_K}$ for the changes from baseline in the primary endpoint capturing the dose-response effect for the doses d_1, d_2, \dots, d_K . This probability model may depend on other (nuisance) parameters and covariates and is described in detail further below.

Subsequently, it is assumed that the dose-response parameters $\mu_{d_k}, k = 1, \dots, K$ are related through a dose-response model $\mu_d = f(d, \theta)$ where $f(\cdot)$ is parameterized by a vector of parameters θ .

Let $\hat{\mu} = (\hat{\mu}_{d_1}, \dots, \hat{\mu}_{d_K})$ denote the vector of estimated dose-response parameters obtained from a parametric model of Y . The key assumption for the generalized MCP-Mod method is that $\hat{\mu}$ has an approximate distribution $N(\mu, S)$, where S denotes the variance-covariance of $\hat{\mu}$. The estimates for $\hat{\mu}$ and \hat{S} are obtained first, while the estimation of θ is done in a separate, second stage based on $\hat{\mu}$ and \hat{S} .

The candidate set of models consists of the $M = 4$ models given by

$$f(d, \theta) = \theta_0 + \theta_1 f^0(d, \theta^0) = -2.3 + E_{max} d^\eta / (ED_{50}^\eta + d^\eta),$$

where d is the dose ranging from 0 mg to 150 mg, θ_0 is a location parameter, and θ_1 is a scale parameter such that only θ^0 determines the shape of the model function, where θ^0 is used to denote parameters associated with $f^0(\cdot)$ component. Guestimates for parameters θ assumed at the trial design stage are listed in Table 1. The two E_{max} models and the two sigmoidal E_{max} models assume a strictly monotonically decreasing dose-response, the illustration of which is provided in the Figure 9–1 in the clinical study protocol.

Table 1: Parameters of the dose-response-curves in the candidate set

Model		Parameters		
Abbreviation	Indicator m	ED_{50}	E_{max}	Hill factor η
emax1	1	25	-1.4	1
emax2	2	100	-2.0	1
sigEmax1	3	35	-1.2	3
sigEmax2	4	75	-1.2	5

Analysis

Step 1: Estimation of μ and S from a mixed model for repeated measures with covariate adjustment

The expected dose response at the tested dose levels will be captured by the adjusted model-based treatment group means of the primary variable's values obtained from a mixed model for repeated measures (MMRM). Absolute change in mean worst EAPP from baseline to each post-baseline time point will be modeled as the dependent variable. The model will include fixed effects for treatment group (four treatment groups: placebo group and 25 mg, 75 mg, and 150 mg BAY 1817080), time point (Visits 3, 4, and 5), time point by treatment group interaction, region (Japan vs. ROW excluding China), and baseline EAPP as continuous covariate. An unstructured variance-covariance pattern will be used to model variance-covariance of the within-subject errors. This variance-covariance matrix will be estimated across treatment groups. In case the model does not converge, alternative variance-covariance structures will be considered. Variance-covariance parameters will be estimated using Restricted Maximum Likelihood (REML) with the Newton-Raphson algorithm and using Kenward-Roger method for calculating the denominator degrees of freedom and adjusting standard errors.

Least squares means for each treatment group at Visit 5 will be estimated from the time point by treatment group interaction term together with their variance-covariance matrix and will represent $\hat{\mu}$ and $\hat{\Sigma}$, respectively. The 80% CIs will also be estimated.

Absolute change in mean worst EAPP from baseline to post-baseline Visits 3, 4, and 5 may be missing for some participants due to a lack of compliance with eDiary completion. All such missing data and data that are unobservable after IEs intended to be addressed by a hypothetical strategy, as described in the primary estimand definition in Section 6.2.1, will be assumed to be Missing at Random (MAR) and will be modeled as such using the MMRM described above. That is, values of subjects with missing and unobservable data will be assumed to be distributed similarly to subjects with observed data in their treatment group conditional on the covariates included in the model and on partially observed data.

MMRM analysis will be implemented using SAS Proc MIXED.

Step 2: Detection of dose-response signal

For detecting an overall trend, or a dose-response signal, each of the $M = 4$ dose-response shapes in the candidate set will be tested, using a single contrast test.

For each model m in the candidate set

the null hypothesis $H_{0m}: (\mathbf{c}_m)' \boldsymbol{\mu} = 0$

will be tested against

the respective 1-sided alternative hypothesis, $H_{1m}: (\mathbf{c}_m)' \boldsymbol{\mu} > 0$

where $\mathbf{c}_m = (c_{m1}, \dots, c_{mK})'$ is the optimal contrast vector representing model m .

The optimum contrast coefficients and critical values for the four contrast tests on the dose-response shapes will be derived based on the guestimates for parameters $\boldsymbol{\theta}^0$ of standardized versions of the models in the candidate set specified at the design stage, the actual sample size for each treatment group after study completion, and the covariance matrix $\hat{\Sigma}$ estimated from actual data using the MMRM described above [6].

Each dose-response model m will be tested using a single contrast test:

$$T_m = (\mathbf{c}_m)' \hat{\boldsymbol{\mu}} / [(\mathbf{c}_m)' \hat{\mathbf{S}} \mathbf{c}_m]_{m,m}^{1/2}$$

where $[A]_{m,m}$ denotes the m^{th} diagonal element of the matrix A .

The final detection of a dose-response signal is based on the maximum contrast test statistic $T_{max} = \max(T_1, \dots, T_4)$ and can be concluded if $T_{max} > q_{1-\alpha}$, where $q_{1-\alpha}$ is the multiplicity adjusted critical value at level $\alpha = 0.1$. The MCP-Mod method takes multiplicity into account, and no further multiplicity adjustments are needed.

If no candidate model is statistically significant, the procedure stops indicating that a dose-response relationship cannot be established from the observed data. If, on the other hand, there is one or more models with a significant adjusted p value, these significant models will be retained and fitted as described in the next step.

Step 3: Modeling and estimation of target doses

The selected dose-response models (with a significant dose-response trend detected at the previous step) will be fitted to $\hat{\boldsymbol{\mu}}$ and $\hat{\mathbf{S}}$ to estimate the model parameters $\boldsymbol{\theta}$ using a generalized least squares (GLS) estimation criterion [6].

If multiple models have significant adjusted p-values at Step 2 and can be successfully fitted (without convergence or numerical stability issues), final inference will be based on the model with the best fit as determined by the AIC criterion.

To estimate the target dose(s) of interest the minimal effective dose (MED) will be determined:

$$MED = \underset{(d=d_1, d_4)}{\operatorname{argmin}} \{ \tilde{f}(d, \hat{\boldsymbol{\theta}}) > \tilde{f}(d_1, \hat{\boldsymbol{\theta}}) + \Delta \}$$

where $\tilde{f}(d, \hat{\boldsymbol{\theta}})$ is the best estimated model and Δ is the smallest relevant difference, by which a dose is expected to be better than placebo in terms of efficacy measured by the primary efficacy variable.

The MED will be provided for the following smallest relevant differences:

Δ = clinically meaningful threshold (e.g. -1)

Δ = the observed effect of Elagolix in the study

The final choice of the target dose will be based on the analyses of the primary, secondary, and other efficacy variables, as well as safety considerations

MCP-Mod related steps 2 and 3 will be performed using the R “DoseFinding” package (version 0.9-17 or higher) [7].

The level of significance for statistical testing is set to 10 % one-sided. The type I error will be controlled for the primary analysis only.

In consistency with the one-sided level of significance given the generally two-sided reporting of CIs, 80 % CIs will be reported for the primary analysis and its related sensitivity/supplementary analyses in addition to 95 % CIs.

